## 20.3. Expected adverse events

Expected events from LFS include intra-operative, early post-operative and post-operative complications. Intra-operative expected events can include excessive bleeding/blood loss, vascular injury, peritoneal tear, dural tear, nerve injury, damage to nerve root, damage to spinal cord, Cauda Equina, visceral injury, bowel injury, screw misplacement, implant malposition, loss of swab, bone fracture, loss of purchase of fixation, wrong level surgery as well any other complications associated with the surgical approach. In addition, General Anaesthetic expected events can include additional intra-operative complications i.e. Anaesthetic complications (aspiration, myocardial infarction, air embolism, cardiac problems and death). Further complication can be systemic such as haemorrhage or the need for further surgery over the 24-month period.

Expected early post-operative and post-operative complications include wound infection, thromboses (DVT and PE), bleeding that requires transfusion, CSF Leak, hematoma or clot formation around the nerve or spinal cord, pseudarthrosis, cage or implant movement or migration, malposition of screws, screw cut out, breakage of screws or rods, construct failure i.e. Implant pullout, Junctional problems i.e.: adjacent segment issues, Cauda Equina syndrome, damage to spinal cord, sympathetic nerve damage, damage to nerve root, damage to major blood vessels, scarring around the nerve, loss of bladder/bowel, paralytic ileus, loss of sensations/motor power to legs, warm legs, worsening pain or symptoms, retrograde ejaculation (men only), sexual dysfunction (male and female). In addition, early post-operative and post-operative risk of complications include: stroke, heart attack, death. General Anaesthetic complications include. brain haemorrhage, ischaemic stroke, subarachnoid haemorrhage.

Expected event from BCC include significant unexpected increase in pain due to unaccustomed new exercise programmes, adverse events associated with prescribed medications, damage to the sciatic nerve, allergic reaction (e.g. to medications), infection.

Any expected adverse events related to the procedures will be collected as complication data on a CRF. The central study team will follow up any complications reported by participants with the local research team at participating sites.

In addition, a final readmission checklist will be undertaken by the research staff on participating site records at 24 months post-randomisation to ensure that all complications data are collected from all participants (i.e. those who had not returned a questionnaire). Data from any readmission events (e.g. evacuation of haematoma, revision of metal work (e.g. implant failure, malposition of screws, cage migration), exploration and wash out for suspected infection), which may result in further surgery will be recorded in the Complications Form

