#### 9.2. Primary and secondary objectives and outcome measures

The primary outcome is the Oswestry Disability Index (ODI), a validated LBP physical function disability score, at 24 months (also measured at 6 & 12 months). The ODI is well validated and a commonly used outcome measure in LBP RCTs including surgery and contains 10 items that assess domains including personal care, walking, standing and sleeping.

Secondary outcomes include LBP severity (Numerical Rating Scale), measured using monthly SMS data or by email or paper options dependant on participant preference (over 24 months). We will also collect participant reported outcome measures reported via questionnaires at 6, 12 and 24 months. The participant questionnaires include: quality of life (EQ-5D-5L), depression (PHQ8), fear avoidance beliefs (TSK), pain self-efficacy (PSEQ), work outcomes (days-off-work), comparison of back pain from entering the study to timepoint of questionnaire using Global Perceived Effect Scale (GPE), healthcare use (NHS and non-NHS including concurrent treatments ie: analgesia) and treatment satisfaction measured at 24 months follow-up with scoring 0-10 (with 10 being very satisfied with treatment).

Further secondary outcome measures will be collected throughout the 24 months using specially designed CRF's to be completed by clinicians and researchers regarding surgery, Best Conservative Care (BCC), Surgery complications (intra and post operative), further surgery including re-admission, Fusion Failure (LFS participants only), BCC complications.

Objective	Outcome measure	Time point(s) of evaluation of this outcome measure (if applicable)
1. To test for superiority of	Primary:	24 months (also measured at 6
lumber fusion surgery (LFS)	LBP-related physical function	& 12 months)
versus BCC on disability	using the Oswestry Disability	
(physical function) in	Index (ODI version 2.1b)	
patients with persistent		
lower back pain (LBP)		
	Secondary:	
2. To investigate the cost-		
effectiveness of LFS	LBP severity (Numerical	
compared with best	Rating Scale) monthly – post	
conservative care (BCC)	randomisation	
	Participant reported	
	outcomes	

	measured at 6m, 12m and	
	24m post randomisation:	
	1. Quality of Life: EQ-5D-5L	
	2. Pain Self-efficacy	
	Questionnaire (PSEQ)	
	3. Patient Health	
	Questionnaire (PHQ8)	
	4. Tampa Scale of	
	Kinesiophobia (TSK)	
	5. Global Perceived Effect	
	Scale (GPE)	
	6. Healthcare Resources	
	Use	
	7. Work status	
	8. Treatment Satisfaction	

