## 13.2. Best Conservative Care (BCC) (usual care/ comparator)

All participants randomised to the BCC control arm will be reviewed by a senior spinal practitioner or pain physician, (usually a senior MSK physiotherapist), with experience in delivering personalised spinal care utilising shared decision making (SDM) with links to a wider Multi-Disciplinary Team (MDT). This will include a clinical evaluation of imaging findings, a formulation of the participants case and a review of previous treatment effectiveness. An individually tailored package of care based on the participant's goals and expectations will be agreed through Shared Decision Making (SDM) and labelled as 'Personalised Spinal Care'. In this way the BCC will be personalised and attractive to potential participants.

Treatment options within BCC will be aligned with national guidance (NICE and the NLBRPP) and include at least one of the following:

- 1. Advice (active self-management, pacing, diagnosis, aetiology, return to work etc.)
- 2. Analgesia
- 3. Exercise
- 4. Manual Therapy (manipulation, joint/soft tissue mobilisation)
- 5. Combined Physical & Psychological Programme
- 6. Pain Management Programme
- 7. Psychological Therapy (e.g. Psychologist, Cognitive Behaviour Therapy, ACT, Behavioural Therapist, Counselling)
- 8. Interventional Pain Management for low back pain (e.g. medial branch block/radiofrequency denervation)
- 9. Signposting to other health material or interventions (e.g. Dietician, smoking cessation, social prescribing)

Complex healthcare interventions such as those utilised for the conservative care of those with persistent LBP are frequently composed of multiple independent and interdependent elements. Therefore, slight variations from those listed above but within the accepted framework are

acceptable to reflect local service provision. We have worked with the FORENSIC-UK CAG to closely define essential and preferred treatment components.

If the participant randomised to BCC is placed on a long wait list for BCC treatment options they will continue with the relevant NHS Trust routine care with monitoring until they can commence their BCC treatments.

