#### Participant questionnaires

A study questionnaire will be sent to participants for completion at 6-, 12- and 24-months post randomisation. These will be sent by the central study team and can be completed by post or online. The questionnaire will include the following:

- LBP-related physical function using the Oswestry Disability Index (ODI)
- Quality of life (EQ-5D-5L)
- Pain Self Efficacy Questionnaire (PSEQ)
- Change to back pain measure using Global Perceived Effect (GPE)
- Patient Health Questionnaire (PHQ8)
- Fear of movement (fear avoidance) beliefs (TSK)
- Healthcare resources use (NHS and non-NHS) including surgery, conservative care, concurrent treatments (including analgesia)
- Work Status (days off work)
- Participant Intervention Adherence
- Treatment Satisfaction at 24m only

In addition, LBP severity (Numerical Rating Scale) will be collected using monthly SMS messages which will contain a link to enter a score or by email or by paper version via the post (participant preference) to capture data on low back pain severity. A reminder email/SMS message will be sent 2 days after the initial message, sent from the central study team to participants over the 24 months follow-up period. We will follow up with a postal reminder by post (for participants wishing to complete the LBP pain severity on paper) two weeks after the initial postal form was sent to accommodate postal delivery.

All postal questionnaires including LBP pain severity will be accompanied with a self-addressed stamped return envelope.

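### Section 20.3 lists worsening pain broadly for LFS but narrowly for BCC, and its BCC entry clashes with the protocol's own definition of an unexpected event

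*Protocol*

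**What the plan says.** Section 20.3 of the protocol gives a separate list of expected events for each arm.

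- **LFS.** The post-operative list opens with "Expected early post-operative and post-operative complications include wound infection, thromboses (DVT and PE" and later includes "loss of sensations/motor power to legs, warm legs, worsening pain or symptoms, retrograde ejaculation (men only". The pain item has no severity threshold and no stated mechanism.
- **BCC.** The list opens with the pain item: "Expected event from BCC include significant unexpected increase in pain due to unaccustomed new exercise programmes". It then names adverse events of prescribed medication, sciatic nerve damage, allergic reaction and infection.
- **What the lists are used for.** The same section continues: "Any expected adverse events related to the procedures will be collected as complication data on a CRF".

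Section 9.2 includes complications of both treatments among the further secondary outcomes: "Surgery complications (intra and post operative), further surgery including re-admission, Fusion Failure (LFS participants only), BCC complications". Section 13.2 gives nine BCC options, of which at least one is delivered. Exercise is one. Others are "Manual Therapy (manipulation, joint/soft tissue mobilisation" and interventional pain management such as medial branch block or radiofrequency denervation.

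Table 4 in section 20.2 treats an event as unexpected when the protocol does not list it as an expected occurrence. Section 20.7 sends related, unexpected SAEs to the ethics committee within 15 days. Section 22.3 presents adverse events descriptively.

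**The concern.** Participants enter with back pain of at least 6 out of 10, so worsening pain is an obvious harm that either treatment could cause. It is also one of the few harms that can be compared directly between surgery and conservative care. If the entry that prompts sites to record it is broad in one arm and narrow in the other, part of any difference in complication counts will come from the wording.

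Site staff and participants know the allocation, so blinded assessment cannot offset arm-specific wording. The DSMC reviews safety by treatment group and may recommend pausing or stopping on safety grounds (Table 3 and section 22.7). Any distortion would run against LFS, both there and in the final harms summary. A later analysis plan cannot recover events that sites were not prompted to record.

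A second problem is one of logic. The BCC item places an event described as unexpected on the list of expected events, although under Table 4 being listed is what makes an event expected. A site cannot apply the two together.

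**Working it through.** This is mainly a comparison of texts. The plan gives no figure for pain worsening.

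**Step 1: which related events fit a listed entry.** The rule in 20.3 covers events that are expected and related to the procedures, in both arms.

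| Event | LFS list | BCC list |
|---|---|---|
| Related pain worsening, significant, from new exercise | Fits | Fits, but the item calls it unexpected |
| Related pain worsening, below significant | Fits | Does not fit the pain item |
| Related pain worsening after manual therapy or denervation | Counterpart after surgery fits | Does not fit the pain item; fits another entry only if it comes from nerve damage, infection or an allergic reaction |
| Adverse event of prescribed medication | No such entry | Has its own entry |
| Worsening unrelated to treatment (natural course) | Not collected under this rule | Not collected under this rule |

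The arms differ in the second and third rows. They agree in the last.

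**Step 2: other routes to the complications form.** Participant-reported complications are followed up with sites in both arms, and a readmission check is made for everyone at 24 months (sections 17.3 and 20.3). The first could catch some BCC pain events. The second catches only those that led to readmission.

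**Step 3: expectedness of a serious, related pain worsening** (Table 4 with section 20.7).

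- After LFS it is listed, so it is expected and not subject to the 15-day report.
- After manual therapy or denervation in BCC it is not listed, so it is unexpected and reportable.
- After new exercise in BCC it is listed, hence expected, yet the item calls it unexpected. The text gives both answers.

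**Step 4: what the wording could do to counts.** The only figure taken from the plan is 135 per arm. It reproduces: a t-test calculation for 8 points, SD 18, two-sided 5% and 90% power gives 108 per arm, and 108 / 0.8 = 135. Everything else here is assumed. Let w be the same true proportion in each arm with related pain worsening, and q the share of BCC cases recorded. Assume all LFS cases are recorded. Then the LFS count is 135 × w, the BCC count is 135 × w × q, and the artificial excess is 135 × w × (1 − q).

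| w | LFS | BCC, q = 25% | BCC, q = 50% | BCC, q = 75% | Excess (q = 75% to 25%) |
|---|---|---|---|---|---|
| 10% | 13.5 | 3.4 | 6.8 | 10.1 | 3.4 to 10.1 |
| 20% | 27.0 | 6.8 | 13.5 | 20.3 | 6.8 to 20.3 |
| 30% | 40.5 | 10.1 | 20.3 | 30.4 | 10.1 to 30.4 |

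With q = 100% the excess is zero. The table shows how the count responds to w and q. It is not an estimate for this trial.

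**The case against.** The strongest case on the other side is that this is a drafting slip with little consequence. Several parts of it stand.

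- **Relatedness applies to both arms.** The LFS item is not free of any causal condition, because only procedure-related events are collected. Pain that drifts upward under continued care qualifies in neither arm.
- **The lists are open.** Both say *include*, so a site may record a BCC pain event that does not match the wording. A reader might infer that such events are counted after surgery and never counted in BCC (13.5 against 0 at an assumed 10% rate). The documents do not support that. Zero is the bound under the strictest reading, on an assumed rate.
- **Some BCC pain has another entry.** Events due to prescribed medication, nerve damage or infection are listed in their own right.
- **Pain is already compared evenly.** "LBP severity (Numerical Rating Scale) will be collected using monthly SMS messages", with email or paper as alternatives, in both arms over 24 months. The ODI and global perceived effect are also collected in both arms. Adverse events are only described, and section 9.2 names surgical and BCC complications as separate items.
- **The expectedness effect is narrow.** It concerns only serious, related events, and it tends to send more BCC events to the ethics committee.
- **Documents not shown.** The complications CRF and the DSMC report template may use different wording.

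These points limit the size of the problem. They do not make the two entries equivalent, supply a common definition, or resolve the clash with Table 4. Even treatment of mean pain scores also does not make the recording of complications even.

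**Conclusion.** The point holds as a fault in the protocol's wording that should be corrected. Followed as written, 20.3 gives intervention-related pain worsening a clear place on the complications form after LFS. After BCC it does so only when the increase is significant and due to new exercise. The likely result is some under-recording in BCC and an apparent excess in LFS. The direction follows from the text, provided sites are guided by the lists. The size cannot be derived from the documents and could be small if sites record beyond the listed items.

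The conflict between the BCC item and Table 4 needs no assumption: the two passages contradict each other and must be reconciled.

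The primary ODI analysis and the NRS comparison are untouched. What is affected is the comparability of complication data between arms, the by-arm safety review, and the classification of a small set of SAEs.

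**What to change.** In section 20.3, replace the two pain items with one entry for intervention-related pain worsening, worded identically for LFS and BCC. Remove *unexpected* and the restriction to new exercise from the BCC item. If a severity qualifier is kept, define it and apply it to both arms. Use that one entry for the complications CRF and for judging expectedness under Table 4 and section 20.7. Report pain worsening by randomised arm in its own line, apart from procedure-specific complications such as implant or wound problems.

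The cost is a change of wording in 20.3, a matching check of the complications CRF, and one extra descriptive line. No new data are needed. A summary of worsening from the monthly NRS, using the same pre-stated rise in both arms, would be a useful addition but is optional. Making the change early matters most, since events not prompted for at sites are hard to recover later.

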# 20.4. Reporting of SAEs from sites to the CTU study team

Only serious adverse events considered by the site investigator to be related (possibly, probably, or definitely) to the study intervention will be reported immediately to the central study team. Such events will be reported immediately to the Study Office as follows:

SAEs will be reported by the local site research team using the SAE form within the REDCap study database, within 24 hours of becoming aware of the event. The CTU is automatically notified of the SAE report through the database. A paper SAE form should be used as a back-up if the SAE form is not available electronically. This should be e-mailed to [contact] within 24 hours of becoming aware of the event. The central CTU study team will acknowledge receipt of any SAEs reported via e-mail within one working day and provide the site with a unique SAE Log number.

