#### 9.3. Choice of primary outcome

The Oswestry Disability Index (ODI) is a well validated and commonly used outcome measure in low back pain (LBP) RCTs including surgery, contains 10 items that assess domains including personal care, walking, standing and sleeping.

Follow-up at 24 months after randomisation allows participants in both arms to reach at least 1 year follow-up after intervention taking into account treatment waiting lists.

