## 13.3. Change of Management

Change of allocated intervention from BCC to LFS is not possible as LFS is not a commissioned intervention in the NHS. However, it is possible that a limited number of participants allocated to LFS may not undergo the surgery during the trial (in line with usual surgical care more generally) and some may not take up the offer of BCC. These changes of management will be investigated in the QRI, and our aim is to keep these to a minimum. Change of management for both arms will be monitored and accounted for in the secondary analysis.

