#### **Medical notes check**

The central study team will follow up any complications reported by participants with the local research team at participating sites. Details will be collected and recorded on a complications form.

In addition, a final readmission checklist will be undertaken by the research staff on participating site records at 24 months post-randomisation to ensure that all complications data are collected from all participants (i.e. those who had not returned a questionnaire). Data from any readmission events e.g. revision/further surgery identified will be recorded on the Complications Form.

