## **BLINDING AND CODE BREAKING**

Participants and clinicians delivering the interventions will not be blinded to intervention allocation due to the nature of the interventions.

Table 3: provides an overview of the blinding status of all individuals involved in the conduct and management of the study.

Role in study	Blinding status	Additional information
Participants	Not blinded	It is not possible to blind due to the nature of the
		interventions. Participants will be told their treatment
		allocation immediately after randomisation.
Site clinical and	Not blinded	It is not possible to blind due to the nature of the
research staff		interventions. Following randomisation, an email will be
including Principal		sent to the members of the site research team, as
Investigator		applicable, performing the randomisation (as delegated)
		confirming treatment allocation.
Chief	Blinded, except	The Chief investigator will remain blinded to treatment
Investigator(s)	for any SAE	allocation overall (knowledge of treatment allocation is
	causality	limited to participants at their own site). In instances
	assessment.	where serious adverse events are reported, the CIs will
		become unblinded to complete the full causality
		assessment.
Database	Not blinded	The database programmer is responsible for the
programmer		management of RRAMP randomisation system and the
		REDCAP database and will have access to all unblinded
		datasets within both systems.
FORENSIC-UK	Not blinded	Study Management staff within FORENSIC-UK study
Study Management		team will not be blinded to treatment allocations as site
staff within		staff may require support for randomisation, or
FORENSIC-UK study		participants may contact the study team directly. Serious
team		Adverse Event reports will also be handled by the study
		management team which will contain allocation
-		information.
Data Management	Not blinded	Data management staff will have access to the unblinded
		datasets within the study randomisation system and
		database to ensure data quality and undertake central
		monitoring activities.

Table 3: Blinding status of those involved in study	y conduct and management.
---	---------------------------

Study statistician and Senior Study Statistician	Not blinded	The study statistician and senior study statisticians will have access to treatment allocations or data needed for generating the Data Monitoring Committee (DMC) closed reports and the final analysis.

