#### 20. SAFETY REPORTING

#### 20.1. Safety reporting period

Safety reporting for each participant will begin from the first point of administration of the intervention i.e. lumbar fusion surgery or best conservative care and will end when the participant has reached their final main follow-up time point, at 24 months post-randomisation (including period for CT scan at 24 months for participants who have undergone Lumbar Fusion Surgery).

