#### Table 4: Safety reporting definitions

An adverse event (AE)	Any untoward occurrence in a trial participant. An AE can therefore be any unfavourable and unintended sign (including an abnormal laboratory finding, for example), symptom or disease temporarily associated with study procedures, whether or not considered related to the procedures.
Related Adverse	An event that resulted from administration of any of the research
Event	procedures
Serious Adverse	An AE that:
Event (SAE)	
 
results in death
 
is life-threatening
 
requires hospitalisation or prolongation of existing hospitalisation
 
results in persistent or significant disability or incapacity
 
is a congenital anomaly or birth defect
 
is otherwise considered medically significant by the Investigator
 

Unexpected Related Serious Adverse Event	A serious adverse event related to the study (i.e. resulted from administration of any of the research procedures) and is unexpected (not listed in the protocol as an expected occurrence).

 Participant was at risk of death at the time of the event; it does not refer to an event which hypothetically might have caused death if it were more severe

 Medical events that may jeopardise the participant or may require an intervention to prevent one of the above characteristics/consequences.

A distinction is drawn between serious and severe AEs. Severity is a measure of intensity whereas seriousness is defined using the criteria above. Hence, a severe AE need not necessarily be serious.

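### Sections 20.1 and 20.4 do not provide for reporting deaths judged unrelated or deaths before treatment starts, and no other route states that all-cause deaths are recorded from randomisation in both arms

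*Protocol*

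**What the plan says.** Four provisions of the protocol combine here.

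- **What is reported.** On what sites send to the central team, Section 20.4 states: "Only serious adverse events considered by the site investigator to be related (possibly, probably, or definitely) to the study intervention will be reported immediately". The time limit is 24 hours. Table 4 counts an event that "results in death" as an SAE, and Section 20.4 does not exempt deaths.
- **Who decides.** Section 20.5 gives the causality judgement to the site principal investigator or a designee. The blinding section states: "Participants and clinicians delivering the interventions will not be blinded to intervention allocation due to the nature of the interventions". Table 3 lists site clinical and research staff, including the principal investigator, as not blinded.
- **When it starts.** Section 20.1: "Safety reporting for each participant will begin from the first point of administration of the intervention".
- **What can come before that.** Section 9.3 says that 24-month follow-up "allows participants in both arms to reach at least 1 year follow-up after intervention taking into account treatment waiting lists". Section 13.3 adds that "it is possible that a limited number of participants allocated to LFS may not undergo the surgery during the trial", and that some participants may not take up BCC.

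Table 3 has the DSMC reviewing safety by treatment group. Sections 22.7 and 25.4 let it recommend stopping for safety reasons.

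**The concern.** The trial compares surgery under general anaesthesia with non-surgical care, and nobody at site is blinded. Counts of related SAEs by arm then reflect two things: how often harm occurs, and how readily staff who know the arm attribute it to treatment. All-cause death counted from randomisation depends neither on attribution nor on when treatment began. It is the safety measure least exposed to knowledge of the allocation, and it matches the as-randomised comparison in Section 22.3.

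Sections 20.1 and 20.4 filter deaths on both counts: by relatedness, and by whether treatment had started. At stake is whether the DSMC can rely on a complete count of deaths in each arm. This is not a matter for the statistical analysis plan, because an analysis can only count what Section 20 causes to be collected.

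**Working it through.** The plan gives no figure on this point, so the check is to follow each kind of death through the rules as written.

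**Step 1: the SAE route (Sections 20.1, 20.4, 20.5 and 20.6, Table 5).** Table 5 treats possibly, probably and definitely as related, and unlikely as unrelated.

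| Death | Inside the 20.1 period? | Sent to the central team as an SAE under 20.4? |
|---|---|---|
| After treatment starts, judged at least possibly related | Yes | Yes, within 24 hours |
| After treatment starts, judged unrelated or unlikely | Yes | No |
| While waiting for allocated treatment | No | No |
| Participant never starts allocated treatment | No | No |

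Section 20.6 assumes an event is related when the site gives no causality assessment. That acts only on events already reported, so it cannot recover a death that the site has filtered out.

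**Step 2: could another stated route fill the last three rows?**

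- *Complications CRF (20.3).* It takes expected events related to the procedures. Death is listed as expected for surgery and anaesthesia but not for BCC, so the route is not symmetrical.
- *Clinician-completed CRFs (9.2).* Besides surgical complications they cover "further surgery including re-admission, Fusion Failure (LFS participants only), BCC complications". Death is not named.
- *Participant-reported complications (Medical notes check, 20.3).* These depend on the participant reporting.
- *24-month site-record check (Medical notes check, 20.3).* It covers all participants, including those who returned no questionnaire. Its stated content is complications and readmissions: "Data from any readmission events e.g. revision/further surgery identified will be recorded on the Complications Form". Deaths may come to light here, but vital status is not a stated item.
- *Safety reporting row in Table 2 (6, 12 and 24 months).* It is separate from the complication-data row, and its content is undefined. It neither includes nor excludes deaths.
- *Withdrawal CRF (17.5).* It records reasons for withdrawal. Death is not named, and SAEs are referred back to the safety section.
- *Reasons for missing data (22.9).* These are described where available, with counts by arm. A known death could appear here, but nothing requires deaths to be ascertained.
- *Routine-data linkage (10.10, 28.1).* It is for long-term outcomes and subject to further funding. Deaths are not mentioned.

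Several of these could reveal a death. None states that deaths from any cause are recorded from randomisation in both arms.

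**Step 3: the wait.** Section 9.3 expects at least 12 months of follow-up after intervention within 24 months of randomisation. The wait allowed for is therefore at most 24 − 12 = 12 months. This is a planning ceiling, not an expected wait, and the protocol does not say whether waits differ by arm.

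**Step 4: scale.** The protocol gives no death, SAE or attribution rate. As an assumption only, take annual mortality of 0.1% to 0.5% in adults aged 18 to 65. Ignoring loss to follow-up, 270 participants × 2 years = 540 person-years. Expected deaths in both arms together are then 540 × 0.001 = 0.54 to 540 × 0.005 = 2.7. Only some of these would fall in the last three rows of the table.

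**The case against.** The strongest reply is that Section 20.4 governs only what is reported immediately and does not forbid recording other events later. Restricting expedited reports to related SAEs is a legitimate choice within the risk-adapted approach of Section 25.1. Form content can sit in the Data Management Plan, and DSMC content in its charter. Table 4 defines an adverse event without regard to relatedness, and the safety reporting row in Table 2 is not limited to complications. The threshold for relatedness is low, since possibly is enough. The site-record check covers everyone, and both arms are monitored while waiting (Sections 13.1 and 13.2). With so few deaths likely, a comparison by arm would say little.

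Most of this stands, and it rules out several stronger readings that a reader might infer:

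- *That unrelated deaths go unrecorded.* Not supported: several routes may capture them, and one is undefined rather than closed.
- *That the 24-hour rule is itself wrong.* It is acceptable and should stay.
- *That safety results are biased in a known direction.* The protocol gives nothing from which to derive a size or direction.
- *That a large part of follow-up goes unmonitored.* The 12-month wait is only a ceiling, and the clinician CRFs run throughout the 24 months.
- *That the checklist drops admissions not leading to further surgery.* Section 20.3 has a trailing clause that could be read so, but it also speaks of any readmission event, as does the Medical notes check.

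What the reply does not remove is that Sections 20.1 and 20.4, followed as written, leave out identifiable groups of deaths, and that no other section expressly covers them.

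**Conclusion.** The point holds as a gap in the stated safety rules. Deaths judged unrelated by unblinded site staff are not reported to the central team as SAEs. Deaths before treatment starts, or in participants who never start it, fall outside the safety period. No other route commits the trial to recording all-cause deaths from randomisation in both arms.

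The size of any effect is unknown and probably small. The range of about 0.5 to 2.7 deaths in total rests on assumed mortality rates that are not in the protocol. The primary ODI result is not affected. The change is still worth making: when deaths are few, one missed or differently attributed death can alter what the DSMC sees, and the remedy costs very little. The conclusion rests on the protocol alone; if the DSMC charter or the case report forms already require all-cause deaths, the change only brings the protocol into line with them.

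**What to change.** 1. **Section 20.4:** keep 24-hour reporting for related SAEs. Add that deaths from any cause, from randomisation to 24 months and in both arms, are reported to the Study Office and made available to the DSMC by arm.
2. **Section 20.1:** state that for deaths the reporting period starts at randomisation.
3. **24-month checklist (Medical notes check and Section 20.3):** add a vital-status field, with date and cause of death where known.

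Aligning the readmission wording of those two sections would be tidy but is optional. Expedited reporting of unrelated non-fatal SAEs is not needed, nor is a new requirement to record every unplanned admission. The cost is one sentence, one clause and a few form fields on a check already planned for every participant.
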